6.1 Drug Supplies and Accountability

It is the responsibility of the Sponsor to ensure that study drugs provided for this study are manufactured under Good Manufacturing Practice (GMP) and are suitable for human use. The Sponsor is responsible to ship a sufficient amount of dosage units to allow the clinical site to maintain an appropriate supply for the study.

The study drugs will be stored at the clinical site as per GCP and local requirements in a locked, temperature-controlled room with restricted access. IP vials and any secondary packaging (if applicable) will be labeled according to applicable local regulations.

For full detail on study drug dispensation, storage, handling, and disposal, please refer to the Pharmacy Manual.

6.2 Identification of Treatments

Sixteen healthy volunteers (8 receiving each formulation) will receive one of the following treatments, according to the randomization scheme:

Group A: 400 mg of 100 mg/ml AIO-001 (as Formulation A), AIO-001 antibody as the active ingredient CCI [REDACTED]

Group B: 400 mg of 182 mg/ml AIO-001 (as Formulation B): AIO-001 antibody as the active ingredient CCI

6.3 AIO-001 Randomization and Blinding

This study will be an open-label study due to the objective nature of the data. Subjects will be administered each treatment according to the block randomization scheme. Randomization will be performed on Day 1 by the pharmacy personnel as per site standard process and will be conducted manually via a printed randomization schedule/scheme provided to site.

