1.3 Summary of Clinical Experience

1.3.1 Clinical Safety

As of 09 May 2023 (data cut-off date), Hengrui Pharmaceuticals Co., Ltd has initiated 3 clinical studies (two Phase I and one Phase II) of AIO-001 (SHR-1905). Two clinical studies (SHR-1905-101 and SHR-1905-201) were performed in China, and the other one (SHR-1905-I-101-AUS) was conducted in Australia. A total of 147 subjects received AIO-001, including 100 healthy subjects were exposed to AIO-001 (n=80) or placebo (n=20) at a single dose of 50 - 600 mg, 12 patients with mild asthma received a single subcutaneous dose of 200 mg AIO-001 (n=8) or placebo (n=4), 24 patients with moderate or severe asthma received a single subcutaneous dose of 100/600 mg AIO-001 (n=16) or placebo (n=8), and 11 patients with severe asthma received multiple subcutaneous doses of CCI AIO-001 or placebo.¹

Among 100 healthy subjects exposed to AIO-001/placebo, 63 subjects (63.0%) experienced TEAEs, which occurred in $\geq 5\%$ of the subjects included blood thyroid stimulating hormone increased, blood uric acid increased and blood bilirubin increased (7.0% each), bilirubin conjugated increased, aspartate aminotransferase increased, headache and alanine

aminotransferase increased (6.0% each), and haemoglobin decreased and blood creatine phosphokinase increased (5.0% each).¹

Among 47 patients with asthma who were exposed to AIO-001/placebo, the incidence of TEAEs was 31.9% (15/47), including alanine aminotransferase increased, blood creatine phosphokinase increased, blood uric acid increased and triiodothyronine free increased (2 subjects each), and the others were seen in single subjects.¹

All TEAEs above were mild or moderate in severity, which can be controlled with or without medical intervention. No subjects experienced serious adverse events (SAEs) or fatal TEAEs. No subjects withdrew from studies due to TEAEs.¹

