1.5 Benefit/Risk Assessment

The inclusion and exclusion criteria have been chosen to select subjects who are known to be free from any significant illness, history of autoimmune diseases, and from any condition that could impact their safety or interfere with meeting the study objectives. The proposed safety screening and monitoring assessments are deemed to be sufficient to monitor potential risks of AIO-001 administration. There is no anticipated therapeutic benefit for the healthy subjects in this study.

So far, as mentioned before, a total of 147 subjects received AIO-001/placebo, including 100 healthy subjects were exposed to AIO-001 or placebo (n=20) at a single dose of 50 – 600 mg, 12 patients with mild asthma received a single subcutaneous dose of 200 mg AIO-001 (n=8) AIO-001 or placebo (n=4), 24 patients with moderate or severe asthma received a single subcutaneous dose of 100/600 mg AIO-001 (n=16) or placebo (n=8), and 11 patients with severe asthma received multiple subcutaneous doses of [REDACTED] mg AIO-001 or placebo. [REDACTED]

All the safety data obtained so far was with AIO-001 using Formulation A. Although this is the first time the new Formulation (Formulation B) will be tested in humans, this study will evaluate Formulation B, and a similar safety profile is expected. All excipients are generally recognised as safe. The information obtained in this study may help in the treatment of future patients with severe, uncontrolled asthma.

2. Objectives

Primary objective:

- To compare the safety and tolerability of 400 mg of AIO-001 as the new formulation (Formulation B) with a 400 mg dose of AIO-001 administered as the original formulation (Formulation A) in healthy volunteers.

Secondary objectives:

- To evaluate the PK of a single SC AIO-001 dose of Formulation A in healthy volunteers.
- To evaluate the PK of a single SC AIO-001 dose of Formulation B in healthy volunteers.
- To evaluate the immunogenicity of AIO-001 in healthy volunteers.

3. Endpoints

Primary endpoints:

- Adverse events (AEs), vital signs measurements (blood pressure, heart rate, respiratory rate, and tympanic temperature), 12-lead electrocardiogram (ECG) recordings, physical examinations, and clinical laboratory test results, including hematology, biochemistry, and urinalysis.

Secondary endpoints:

- PK endpoints may include but are not limited to AIO-001 concentrations, $AUC_{0-\text{last}}$, $AUC_{0-\text{inf}}$, C_{\max} , T_{\max} , $T_{1/2}$.

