8.2 Safety and Tolerability Assessments

Subjects will be monitored throughout the study by the clinical staff for AEs. Adequate medical surveillance will be assured during the confinement period and the Investigator or designee will be available on call at all times. If necessary, the Investigator or designee at the clinical site or a healthcare professional in a nearby hospital will administer treatment for any AE(s). A crash cart or emergency bag containing the necessary rescue material and appropriate medications will be available in the clinic to allow rapid intervention in case of emergency.

Safety parameters will be assessed by the Investigator or designee, using the clinical site acceptance ranges as suggested guidelines in making the medical assessment.

For eligibility purposes, abnormal vital signs measurements or clinical laboratory test results may be repeated once if an abnormal result is observed at the initial reading. Moreover, abnormalities found in the ECG may need to be confirmed by repeated measurements. In the event that the participation of a subject in the study is delayed and some screening procedures had been performed outside of the prescribed screening window, outdated screening procedures can be repeated.

Safety assessments scheduled during the study will be repeated according to the clinical site local guidance or upon request from the Investigator or designee. Any abnormal repeated measurement will be evaluated and repeated, if judged necessary. Further action may be taken upon the Investigator or designee's request.

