8.3 Adverse Events

8.3.1 Definition of Adverse Event

An AE is defined as any untoward medical occurrence in a patient or clinical trial subject administered a pharmaceutical product and which does not necessarily have a causal relationship with the treatment. An AE can, therefore, be any unfavorable and unintended sign (including an abnormal laboratory finding, for example), symptom, or disease temporally associated with the use of a medicinal (investigational) product, whether or not considered related to the medicinal (investigational) product.

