3.4 Blinding

This is an open-label study; blinding is not applicable.

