9.1 Laboratory Evaluations

Laboratory data, including hematology, biochemistry, coagulation, and urinalysis (quantitative and categorical), will be listed by subject, and summarized by treatment and visit, categorical values less than x or greater than x will be summarized by frequency. Observed values and changes from baseline will be presented.

In addition, a shift table representing the categorical change (normal, abnormal not clinically significant, or abnormal clinically significant) from baseline to each post baseline visit will be presented by treatment.

Abnormal results will be flagged in the listings.

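### Protocol 6.3 calls the data objective, but part of the primary safety comparison is unblinded judgement, and the laboratory, vital-sign and ECG shift tables have no direction and no judgement-free category

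*Protocol*

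**What the plan says.** - Protocol 6.3 gives the reason for open label: "This study will be an open-label study due to the objective nature of the data". SAP 3.4 adds only: "This is an open-label study; blinding is not applicable".
- The primary objective (Protocol 2) compares the safety and tolerability of the two formulations. The primary endpoints (Protocol 3) are AEs, vital signs and "12-lead electrocardiogram (ECG) recordings, physical examinations, and clinical laboratory test results, including hematology, biochemistry, and urinalysis".
- AE severity is graded on descriptive terms (Protocol 8.3.3, Table 5), and causality is a medical judgement (8.3.4). An AE may be "any unfavorable and unintended sign (including an abnormal laboratory finding, for example" (8.3.1), with no numeric threshold for when a result becomes one.
- Injection-site pain and tenderness are graded by a trained observer who is not said to be masked, and a global rating enters the AE assessment (8.2.3).
- SAP 9.1 Laboratory Evaluations plans "a shift table representing the categorical change (normal, abnormal not clinically significant, or abnormal clinically significant) from baseline to each post baseline visit". SAP 9.2 Vital Signs and 9.3 ECGs use the same three categories. (The SAP uses the numbers 9.1 and 9.2 twice; the second use is meant here.)
- All three sections also plan observed values and changes from baseline, summarised by treatment.
- Under Protocol 8.2 the investigator or a designee assesses safety parameters, "using the clinical site acceptance ranges as suggested guidelines in making the medical assessment".

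**The concern.** The stated reason for open label covers only some of the primary endpoints. Where an endpoint is a judgement, the person judging can know the formulation, and so can the subject who reports pain.

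The laboratory, vital-sign and ECG values are objective when recorded. The planned shift tables then pass them through a clinical-significance call with no fixed criterion. If that call is made more or less readily for one formulation, the shift tables carry the same leaning as the AE tables and cannot act as a separate categorical check on them.

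The categories also have no direction: a rise in one arm and a fall in the other can look the same. Formulation B is being given to humans for the first time and is intended for a proposed phase 2 trial (Protocol 1.4, 1.5), so these tables will be read closely even though no test is planned.

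**Working it through.** The documents give no figure to reproduce: SAP 3.1 states that no formal sample size calculation was made. The check is mainly a comparison of texts.

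**1. Does the stated reason fit each kind of data?**

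| Data | Source | Does the reason fit? |
|---|---|---|
| PK and ADA assays (secondary) | Protocol 3 | Yes |
| Recorded laboratory, vital-sign and ECG values | Protocol 8.2.4 to 8.2.6 | Yes |
| AE reporting, severity, causality | Protocol 8.3.1 to 8.3.4 | No |
| Injection-site pain and tenderness | Protocol 8.2.3, Table 3 | No |
| Clinical-significance category in the shift tables | SAP 9.1 to 9.3 | No |

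**2. Who assigns the category?** SAP 9.1 to 9.3 do not say. Protocol 8.2 gives the assessment of safety parameters to the investigator or designee, with site ranges as guidance only. Neither document provides a masked assessor, a masked central ECG reading, or numeric criteria for clinical significance. That the call is unblinded is therefore an inference, though a well-supported one.

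**3. Is there another categorical comparison?** SAP 9.1 mentions frequencies of laboratory values less than or greater than x, but x is undefined and no reference range is tied to it. The clinical-significance shift tables are the only planned change-by-category tables.

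**4. Loss of direction.** As a constructed example, suppose 2 of 8 subjects on B go from normal to a raised TSH, 2 of 8 on A go from normal to a lowered TSH, and all are judged not clinically significant. Both arms then show 2/8 = 25% in the same cell. A subject who goes from low to high within one abnormal category shows no shift at all.

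**5. Scale.** With 8 subjects per arm (SAP 3.3), one subject classified differently moves that arm by 1/8 = 12.5 percentage points.

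For illustration, let the true event rate p be equal in both arms, and let a share q of subjects with an event go unrecorded or be downgraded in one arm only. The expected spurious difference is 100 × p × q points. The chance that at least one of 8 subjects is affected is 1 − (1 − pq)^8.

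| p | q | Expected difference (points) | Chance at least one of 8 is affected |
|---|---|---|---|
| 0.63 | 0.10 | 6.3 | 0.41 |
| 0.63 | 0.20 | 12.6 | 0.66 |
| 0.63 | 0.30 | 18.9 | 0.81 |
| 0.30 | 0.10 | 3.0 | 0.22 |
| 0.30 | 0.20 | 6.0 | 0.39 |
| 0.30 | 0.30 | 9.0 | 0.53 |

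The value p = 0.63 is the TEAE rate in 100 earlier healthy subjects, AIO-001 and placebo pooled (Protocol 1.3.1). The value p = 0.30 and every q are assumptions. For comparison, the exact 95% interval for 5/8 is 24% to 91%, so a bias of this size could not be seen in the data.

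**The case against.** The strongest reply is that a comparison free of the clinical-significance call is already planned: observed values and changes from baseline, by treatment, for all three data types (Protocol 9.5; SAP 9.1 to 9.3). That stands. A reader might infer that the whole primary comparison rests on unblinded judgement; it does not. Two things remain. Summary statistics on 8 subjects do not show how many moved out of range or which way. And under SAP 5.2 an out-of-range value is replaced by a normal repeat, while Protocol 8.2 lets the investigator request repeats, so even the numeric summaries are not wholly free of discretion.

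Second, abnormal results judged not significant are already tabulated, so adding the two abnormal columns gives normal against abnormal. This is largely right, and SAP 5.2 suggests that the laboratory split follows a range. It does not restore direction, and Protocol 8.2 leaves the range as guidance.

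Third, Protocol 1.3.1 might seem to show that laboratory calls will dominate the AE comparison: eight of the nine terms listed are laboratory findings. But the list covers only terms at or above 5%, pooled over AIO-001 and placebo. It says what kinds of event were common, and nothing about bias.

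Fourth, some injection-site data are measured: Table 3 grades erythema and induration by centimetre bands. That is true, but it does not extend to pain and tenderness.

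Last, this is an openly declared open-label study with no inferential safety analysis (Protocol 9.5, SAP 9). No error rate or decision rule is affected. That limits the consequence, but the by-treatment tables are then all that the reader has.

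**Conclusion.** The point holds in a limited form. The reason in Protocol 6.3 does not describe AE reporting, severity and causality or injection-site pain and tenderness. The only categorical change tables for laboratory, vital-sign and ECG data depend on a call that is, by inference from Protocol 8.2, unblinded, and they merge high with low.

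The documents do not support going further:

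- They do not show that bias will occur, which formulation it would favour, or how large it would be. An investigator might be more alert to a first-in-human formulation, or less so because Protocol 1.5 expects a similar safety profile. The 12.5 points per subject and the illustration above give scale only.
- They do not show that open label is wrong. Four injections against two (Protocol 6.4) make masking of subjects impractical, although neither document gives this as the reason.
- They do not show that thyroid results will be left out. SAP 9.1 does not name them, but its list of panels is not exclusive.

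**What to change.** **SAP 9.1 to 9.3.** Add by-treatment shift tables with low / normal / high categories derived by program from the recorded values. Use the laboratory reference ranges for every quantitative safety panel in Protocol Table 4, naming TSH, T3 and T4. Use the site's existing reference ranges for vital signs and ECG intervals; this assumes that the site holds numeric ranges for each measure. The limits in exclusion criterion 9 would not suffice, since they omit respiratory rate, temperature, PR and QRS. State whether the first or the repeat value is classified. Keep the clinical-significance tables or listings alongside.

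**Protocol 6.3.** Reword the rationale so that it does not claim that all data are objective, and note that the differing number of injections makes masking of subjects impractical. State that AE severity, causality, pain and tenderness are unblinded assessments and a limitation of the A versus B comparison. Do not present the new tables as a check on these: a laboratory or ECG shift cannot verify pain, tenderness or causality.

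**Cost.** A few extra programmed tables from data already collected, and a short protocol edit. The tables will show more abnormal cells by direction, some of no clinical importance.

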6.4 Study Drug Administration

The study drug (AIO-001 injection Formulation A or B) will be injected subcutaneously on Day 1. For safety reasons, subjects will be required to remain seated or semi-reclined during dosing.

- Formulation A: Subjects from Group A will receive 400 mg of 100 mg/ml AIO-001, given as 4 X 1.0 ml subcutaneous injections administered within approximately 5 minutes. The four injection sites are two injection sites on each upper arm separated from each other by at least 5 cm.
- Formulation B: Subjects from Group B will receive 400 mg of 182 mg/ml AIO-001 given as 2 X 1.1 ml subcutaneous injections administered within approximately 5 minutes. The 2 injection sites are one on each upper arm.

IP should not be administered on skin disfigurements or lesions such as scars, tattoos, wounds, bruises, redness and hardening. Please refer to Pharmacy Manual for more details.

The start time of the first injection will be called “0” hour.

7. Study Restrictions

7.1 Contraception

Female subjects who are of non-childbearing potential will not be required to use contraception.

Female subjects of childbearing potential who are sexually active with a non-sterile male partner (sterile male partners are defined as men vasectomized for at least 3 months prior to dosing) must be willing to use one of the following acceptable contraceptive methods throughout the study and for 5 half-lives +1 month after the last dose:

- Simultaneous use of hormonal contraceptive (e.g., oral, depot injection, implant, vaginal ring, intrauterine device) or non-hormonal intrauterine device used for at least 4 weeks prior to dosing (must agree to use the same contraceptive throughout the study) and condom for the male partner.

- Bilateral tubal occlusion or ligation, and condom for the male partner, started at least 21 days prior to dosing.
- Abstinence

Female subjects of childbearing potential must not donate ova during the study and for at least 90 days after the dosing.

Male subjects who are not surgically sterile for at least 3 months prior to dosing, and who are sexually active with a female partner of childbearing potential must be willing to use one of the following acceptable contraceptive methods from the first dose and for 5 half-lives +1 month after the last dose:

- Simultaneous use of condom and hormonal contraceptive (e.g., oral, patch, depot injection, implant, vaginal ring, intrauterine device) or non-hormonal intrauterine device used for at least 4 weeks prior to sexual intercourse for the female partner.
- Abstinence

Male subjects (including men who have had a vasectomy) with a pregnant partner must agree to use a condom from the first dose and for 5 half-lives +1 month after the last dose. Male subjects must also be willing not to donate sperm and for 5 half-lives +1 month after the last dose.

Sexual abstinence is considered a highly effective method only if defined as refraining from heterosexual intercourse during the entire period of risk associated with the study treatment. The reliability of sexual abstinence needs to be evaluated in relation to the duration of the study and the preferred and usual lifestyle of the subject.

7.2 Concomitant Medications

Subjects will be required to avoid using any non-study necessitated medications for the timeframes specified below:

- Depot injection or implant of any drug (other than hormonal contraceptives) for 3 months prior to dosing.
- Prescription medications for 4 weeks prior to dosing.
- Any vaccine, including COVID-19 vaccine and live attenuated vaccination, for 30 days prior to dosing.
- Over-the-counter (OTC) medications and natural health products (including herbal remedies such as St. John's wort, homeopathic and traditional medicines, probiotics, food supplements such as vitamins, minerals, amino acids, essential fatty acids, and protein supplements used in sports) for 14 days prior to dosing (with the exception of the occasional use of acetaminophen up to 2 g daily), throughout the study.

No concomitant medications will be allowed during the study, with the exception of hormonal contraceptives, medications required for the medical management of an AE, and medications

exempted by the Investigator on a case-by-case basis that are judged unlikely to affect the PK profile of the study drug or subject safety (e.g., topical drug products without significant systemic absorption).

If a vaccination is required for any reason, it must first be discussed with and exempted by the Investigator on a case-by-case basis to ensure that it does not compromise the PK profile of the study drug or the subject safety.

Medications taken by subjects before dosing will be documented as prior medications and medications taken by subjects after dosing through the last study day will be documented as concomitant medications. Any prior or concomitant medication use, other than the allowed medications stated above, will be reviewed, and evaluated on a case-by-case basis by the Investigator to determine if they affect a subject's eligibility or continued participation in the study, or for potential impact on the study results.

7.3 Drugs, Nicotine, and Alcohol

Subjects will be required to abstain from:

- Drugs of abuse and illicit use of recreational drugs from screening through study end;
- Any nicotine product within 48 hours prior to admission until the end of inpatient stay (Day 3), and 2 hours prior to each outpatient visit. No more than equivalent of 5 cigarettes per day will be allowed.
- Alcohol-based products from 24 hours prior to admission until discharge.

7.4 Diet

Subjects will be required to abstain from:

- Food containing poppy seeds from 24 hours prior to admission.

While confined at the study site, subjects will receive a standardized diet at scheduled times that will not conflict with other study-related activities.

